6.6 Dose Modification

The National Cancer Institute's Common Terminology Criteria for Adverse Events (NCI-CTCAE) version 5.0 will be used to assess toxicities; in addition, a Bayer grading system (see [Table 6-1](#) and [Table 6-2](#)) will be used to assess corneal epitheliopathy and visual acuity changes.

Treatment-emergent (serious) adverse event (TE(S)AE) requiring dose modification (dose omission, infusion interruption, change in infusion rate, dose delay, dose reduction, or permanent discontinuation of study intervention[s]) will be defined as an adverse event that is possibly, probably, or definitely related to study intervention(s) and occur any time during the study.

For dose modification of the study intervention(s) following TE(S)AE's, please refer back to the relevant parent protocol guidelines. These remain valid also under CTCAE V5.0 AE assessment.

Table 6-1: Bayer classification and management of corneal epitheliopathy

	Grade 0	Grade 1	Grade 2	Grade 3	Grade 4
Corneal morphology	No pathologic changes	Any stage of superficial punctate keratitis ^a	Epithelial opacities	Corneal ulcer without risk of acute rupture	Corneal ulcer more severe than Grade 3
			Micro-cysts Micro-deposits Corneal erosion Stromal opacity: non-central	Stromal opacity: central	
Eye treatment ^b	Ocular lubricants at the discretion of investigator in consultation with ophthalmologist	Ocular lubricants; add topical steroids if superficial punctate keratitis shows treatment-emergent progression by ≥ 2 SPK Grades	Intensive treatment with ocular lubricants enhanced with ointments; topical steroids; therapeutic contact lens may be considered at the discretion of investigator in consultation with ophthalmologist	Intensive therapy with ointments; topical steroids; therapeutic contact lens or occlusion recommended at the discretion of investigator in consultation with ophthalmologist	Intensive therapy with lubricants, ointments, topical steroids and antibiotics as needed; occlusion or therapeutic contact lens recommended; amniotic membrane transplant and other locally approved therapies to be considered at the discretion of investigator in consultation with ophthalmologist

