Anetumab ravtansine ^c	No change	No change	Keep treatment dose level and schedule if the ophthalmological exam can be performed as needed; otherwise consider dose reduction by -1 dose level without dose schedule change at the discretion of investigator in consultation with ophthalmologist	1) Decrease dose to -1 dose level (or -2 dose level if event does not resolve to Grade ≤ 2 at the -1 dose level within 21 days) 2) Re-start at the original dose level if the first Grade 3 event resolves to Grade ≤ 2 within 21 days and does not recur 3) If not resolved within 21 days continue at reduced -1 dose level (or -2 dose level) ^d	Discontinue treatment

MTD = Maximum tolerated dose; SPK = Superficial punctate keratitis

a Oxford Schema must be used for grading SPK from stage 0 to V (see Appendix 10.6).

b Other remedial therapies for corneal epitheliopathy may be added or substituted at investigator's discretion or according to the institutional standards.

c Treatment decisions are based on corneal epitheliopathy only, not on visual acuity changes

d If the MTD of anetumab ravtansine is set at 5.5 mg/kg for either cholangiocarcinoma and/or pancreatic adenocarcinoma, only one dose reduction to 4.5 mg/kg will be allowed. If the MTD of anetumab ravtansine is set at 4.5 mg/kg for either cholangiocarcinoma and/or pancreatic adenocarcinoma, no dose reductions will be allowed; toxicities requiring dose reductions in this instance will result in permanent discontinuation of anetumab ravtansine.

Table 6-2: Bayer classification of visual acuity changes

	Grade 0	Grade 1	Grade 2	Grade 3	Grade 4
Visual acuity	No findings, no reporting from the patient	Symptomatic visual acuity loss < 3 lines (ETDRS equivalent ^a)	Visual acuity loss ≥ 3 lines, but < 6 lines (ETDRS equivalent ^a)	Visual acuity loss ≥ 6 lines (ETDRS equivalent ^a)	Visual acuity loss ≥ 6 lines (ETDRS equivalent ^a) leading to blindness

ETDRS = Early Treatment Diabetic Retinopathy Study

^a In the ETDRS chart, each loss of 3 lines corresponds to halving the visual acuity. In other charts, an equivalent amount of visual acuity loss must be reached in order to meet this threshold.

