- There may be situations in which an SAE has occurred and the investigator has minimal information to include in the initial report to Bayer's pharmacovigilance department. However, **it is very important that the investigator always make an assessment of causality for every event before the initial transmission of the SAE data to Bayer's pharmacovigilance department.**
- The investigator may change his/her opinion of causality in light of follow-up information and send an SAE follow-up report with the updated causality assessment.
- The causality assessment is one of the criteria used when determining regulatory reporting requirements.

Follow-up of AEs and SAEs

- The investigator is obligated to perform or arrange for the conduct of supplemental measurements and/or evaluations as medically indicated or as requested by Bayer's pharmacovigilance department to elucidate the nature and/or causality of the AE or SAE as fully as possible. This may include additional laboratory tests or investigations, histopathological examinations, or consultation with other health care professionals.
- New or updated information will be recorded in the originally completed CRF.
- The investigator will submit any updated SAE data to the Bayer's pharmacovigilance department within 24 hours of receipt of the information.

10.3.4 Reporting of SAEs**SAE Reporting to Bayer's pharmacovigilance department via an Electronic Data Collection Tool**

- The primary mechanism for reporting an SAE to Bayer's pharmacovigilance department will be the electronic data collection tool.
- If the electronic system is unavailable, then the site will use the paper SAE data

SAE Reporting to Bayer's pharmacovigilance department via an Electronic Data Collection Tool

collection tool in order to report the event within 24 hours.

- The site will enter the SAE data into the electronic system as soon as it becomes available.
- After the study is completed at a given site, the electronic data collection tool will be taken off-line to prevent the entry of new data or changes to existing data.
- If a site receives a report of a new SAE from a study participant or receives updated data on a previously reported SAE after the electronic data collection tool has been taken off-line, then the site can report this information on a paper SAE form.
- Contacts for paper SAE reporting can be found in the SAE paper template.

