10.6 Appendix 6: Oxford Schema

DEWS	DRY EYE: DIAGNOSTIC TEST TEMPLATE																						
RAPPORTEUR	A.J.Bron	21 st Oct 2004																					
TEST	Grading staining: Oxford Schema																						
TO DIAGNOSE	The scheme is used to estimate surface damage in dry eye.	REFERENCES																					
VERSION of TEST	[V 1]																						
DESCRIPTION	Surface damage to the exposed eye, assessed by staining, is graded against standard charts.																						
NATURE of STUDY	N. A.																						
CONDUCT of TESTS	
Grading Schema: Staining is represented by punctate dots on a series of panels (A-E). Staining ranges from 0-5 for each panel and 0-15 for the total exposed inter-palpebral conjunctiva and cornea. The dots are ordered on a log scale
 
  
 PANEL	GRADE	CRITERIA	
   
 A	0	Equal to or less than panel A	
 
 B	I	Equal to or less than panel B, greater than A	
 
 C	II	Equal to or less than panel C, greater than B	
 
 D	III	Equal to or less than panel D, greater than C	
 
 E	IV	Equal to or less than panel E, greater than D	
 
 >E	V	Greater than panel E	
  
 
Conduct of Test:
 
 • Dye is instilled. • Slit-lamp is set (eg.16 magnification with x10 oculars with Haag-Streit). • Cornea: The upper eyelid is lifted slightly to grade the whole corneal surface, • Conjunctiva: To grade the temporal zone, the subject looks nasally; to grade the nasal zone the subject looks temporally. • (The upper and lower conjunctiva can also be 	PANEL	GRADE	CRITERIA	A	0	Equal to or less than panel A	B	I	Equal to or less than panel B, greater than A	C	II	Equal to or less than panel C, greater than B	D	III	Equal to or less than panel D, greater than C	E	IV	Equal to or less than panel E, greater than D	>E	V	Greater than panel E	Bron Evans Smith 2003.
PANEL	GRADE	CRITERIA																					
A	0	Equal to or less than panel A																					
B	I	Equal to or less than panel B, greater than A																					
C	II	Equal to or less than panel C, greater than B																					
D	III	Equal to or less than panel D, greater than C																					

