6.3.3 Adverse Events

Treatment-emergent AEs (TEAEs)

In this study, treatment-emergent adverse events are defined as adverse events starting or worsening during the treatment period. The treatment period extends from the first date of treatment in this study until the safety follow-up (30 days after the last administration of study treatment).

Coding and grading of TEAEs

TEAEs will be coded using the latest MedDRA version, and toxicity will be graded using NCI-CTCAE v5.0. Corneal epitheliopathy events (classified as corneal disorders) will be graded according to the Bayer Grading System.

Study drug-related AEs

AEs will be reported as study drug-related if they are documented by the investigator as related to any study drug.

AEs of Special Interest (AESIs)

Adverse events of special interest include any corneal epitheliopathy and infusion-related reactions (IRRs).

Reporting of TEAEs

The incidence of TEAEs and TESAEs, as well as drug-related TEAEs and TESAEs will be summarized in descriptive summary tables (number and percentage of participants) by latest MedDRA version SOC and preferred term (PT) and by worst grade for the following:

- Overview of TEAEs
- TEAEs
- TEAEs in descending order of frequency by Preferred Term (PT)
- Study drug-related TEAEs
- Study drug-related TEAEs in descending order of frequency by PT
- TESAEs
- TESAEs in descending order of frequency by PT
- Study drug-related TESAEs
- Study drug-related TESAEs in descending order of frequency by PT
- TE(S)AEs leading to permanent discontinuation
- TE(S)AEs leading to dose interruption

- TE(S)AEs leading to dose reduction
- Overview AEs of special interest

All AEs, TEAEs, TESAEs, and TEAEs leading to discontinuation of study drug will be presented in separate listings. Listings will be provided in all enrolled participants. AEs of special interest will be included in summary tables of AEs and will be presented in data listings.

A summary of deaths during the treatment period and following 30 days after treatment end in this study will be reported for the safety set. A listing of all deaths at any time during the study will be provided in all enrolled participants.

6.3.4 **Laboratory assessments**

The following laboratory parameters will be summarized in all treated participants:

- Hematology: platelet count, red blood cell count (RBC), hemoglobin, hematocrit, white blood cell count (WBC) with differential

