- Clinical chemistry: aspartate aminotransferase (AST), alanine aminotransferase (ALT), total bilirubin, creatinine
- Serum pregnancy test results will be reported through listings

The clinically relevant laboratory parameter changes occurring during the study were to be reported as adverse events (Section 8.2.3 of the clinical study protocol).

For purposes of the safety analysis, only numerical laboratory values (no clinical assessments) will be used for providing severity ranges for the laboratory data. Ranges are described in Bayer internal documentation [4]. Laboratory toxicities assigned by the investigator or reported as AEs will be documented in the AE CRFs and reported in AE tables and listings; these toxicities may include clinical assessments. The incidence of laboratory toxicities will be summarized in frequency tables.

For laboratory assessments with normal ranges, low/normal/high status will be reported in listings as applicable.

6.3.5 **Other Safety Measures**

In addition, all laboratory assessments, vital signs, and ophthalmologic examination results will be presented in data listings. Listings will be reported in all enrolled participants.

7. **Document history and changes in the planned statistical analysis**

SAP version 1.0, dated 23 MAY 2019.

8. **References**

Statistical Analysis Plan

BAY 94-9343/20322

Page: 10 of 10

3. Collett, D. *Modelling Survival Data in Medical Research: Third Edition*. CRC Press. (2015) p. 29.
4. Handling Laboratory Findings in Bayer Oncology Clinical Trials (Internal) 15 FEB 2019

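### Every Oxford stage of superficial punctate keratitis is Bayer Grade 1, so the planned worst-grade tables cannot show progression from stage I to stage V

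*Protocol*

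**What the plan says.** Protocol 6.6, Table 6-1, defines the Bayer scale for corneal epitheliopathy. Its Grade 1 morphology is "Any stage of superficial punctate keratitis". Grade 2 requires other findings: epithelial opacities, micro-cysts, micro-deposits, erosion or non-central stromal opacity. Footnote a adds: "Oxford Schema must be used for grading SPK from stage 0 to V". Appendix 6 gives the stages, the highest being V ("Greater than panel E"). The eye-treatment row of the Grade 1 column separately recognises the case where "superficial punctate keratitis shows treatment-emergent progression by ≥ 2 SPK Grades".

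On analysis, SAP 6.3.3 says: "Corneal epitheliopathy events (classified as corneal disorders) will be graded according to the Bayer Grading System". For the primary endpoint, "treatment-emergent adverse events are defined as adverse events starting or worsening during the treatment period", and the tables are by system organ class, preferred term and worst grade. The SAP does not say how worsening is identified. Under SAP 6.3.5, "all laboratory assessments, vital signs, and ophthalmologic examination results will be presented in data listings". No summary of Oxford stage is planned.

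On recording, protocol 8.3.1 requires adverse events still ongoing from the parent study to be re-entered in the rollover study. The same section makes a condition that began before consent and then deteriorated an adverse event. Protocol 10.3.1 likewise counts a more intense or more frequent pre-existing condition. The follow-up rules in protocol 10.3.3 say: "New or updated information will be recorded in the originally completed CRF".

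**The concern.** The study's purpose is long-term safety, and corneal epitheliopathy is one of its two named adverse events of special interest. Protocol 10.3.5 introduces the Bayer scale because CTCAE may not reflect the severity of these events. Yet across the whole range of superficial punctate keratitis (SPK) the Bayer scale has a single level.

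Participants have already been exposed, and Table 6-1 calls for no change to anetumab ravtansine at Grade 1, so some may plausibly enter with SPK already present. For them, further corneal damage would appear first as a rise in Oxford stage. The protocol requires that stage to be assessed and names a rise of two or more as progression, but no planned table uses it. A reader of the summary tables would see Grade 1 whether the keratitis was mild and stable or had reached the worst stage.

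A second, conditional risk concerns the TEAE count. An SPK event carried in from the parent study did not start in the rollover treatment period, so it becomes a TEAE only through worsening, a term the SAP leaves undefined.

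**Working it through.** The plan states no figure to reproduce, and the study has no sample size or power calculation. The check maps each Oxford stage to its Bayer grade and counts the upward stage changes that alter the grade.

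**Inputs.** Stages 0, I, II, III, IV and V (Table 6-1, footnote a; Appendix 6). Bayer grade of SPK at any stage: 1 (Table 6-1). Named progression: a rise of 2 or more SPK grades (Table 6-1, Grade 1, eye-treatment row), read here as Oxford stages because footnote a grades SPK on that schema.

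**Formula.** With k stages, the number of possible upward changes is k(k − 1)/2.

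1. Entry with SPK at stage I or higher: k = 5, so 5 × 4/2 = 10 upward changes. Both ends of each change are Grade 1, so 0 of 10 alter the Bayer grade.
2. One-stage rises among these: I–II, II–III, III–IV, IV–V = 4. Rises of two or more: 10 − 4 = 6 (I–III, I–IV, I–V, II–IV, II–V, III–V). The largest is I to V, 4 stages.
3. Including stage 0: k = 6, so 6 × 5/2 = 15 upward changes, of which 5 are one-stage and 10 are two or more. Read literally, any stage includes stage 0, and 0 of 15 alter the grade. If stage 0 is instead taken as Bayer Grade 0, the 5 changes out of stage 0 alter the grade and the other 10 still do not.

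| Starting stages | Upward changes | Alter Bayer grade | Rise of 2 or more |
|---|---|---|---|
| I to V | 10 | 0 | 6 |
| 0 to V, stage 0 as Grade 1 | 15 | 0 | 10 |
| 0 to V, stage 0 as Grade 0 | 15 | 5 | 10 |

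These are counts of possible changes, not frequencies.

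**Effect on the TEAE count.** For carried-in SPK that goes from stage I to stage V, the outcome depends on how it is recorded and programmed:

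- The site records a deterioration under protocol 8.3.1 and 10.3.1, and the program accepts it as worsening: counted as a TEAE, displayed as Grade 1.
- The program defines worsening as a higher Bayer grade: not counted.
- The site only updates the carried-in record, following the general rule in protocol 10.3.3, with no date for the deterioration: the onset stays before the first rollover dose, the grade stays 1, and the event is not counted.

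The documents do not say which of these will apply.

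**The case against.** The strongest reply concerns the primary endpoint. A reader might infer that, because the grade does not move, the count of TEAEs must miss progression of SPK. The documents do not support that. The TEAE definition requires no grade increase, and protocol 8.3.1 and 10.3.1 make deterioration an adverse event without any grade condition. The rule about the original CRF page is a general follow-up instruction, and the CRF itself is not among the documents. This reply stands: loss from the count is possible, not a consequence of the plan as written.

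It is also true that new SPK is correctly counted and correctly shown at its Bayer grade. Findings beyond SPK raise that grade, and visual acuity changes are graded separately in Table 6-2. Protocol 6.6 and 10.3.5 keep CTCAE alongside the Bayer scale, although SAP 6.3.3 names only the Bayer scale for corneal events, so no CTCAE-graded corneal table is assured. None of this gives any planned table resolution between SPK stages.

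A further reply is that the study is descriptive, of unpredictable size, and that protocol 9.4.2 makes extra corneal presentations optional. SAP 4.1 also moves subgroups of fewer than 8 to listings. That argues for keeping the addition small. A table on the whole safety set is not a subgroup table, and the staging is already required.

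Finally, one might want the two-stage rise as the definition of corneal worsening. That would go too far. In the protocol it triggers an eye-treatment step; it does not define an adverse event. As a minimum it would exclude 4 of the 10 upward changes, and nobody entering at stage IV could ever qualify. It could therefore narrow the endpoint relative to protocol 8.3.1 and 10.3.1.

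**Conclusion.** The point holds as a gap in the severity summaries. Under SAP 6.3.3 the worst-grade tables cannot distinguish stage I from stage V SPK or show progression between them, and the Oxford data reach the report only as listings. From stage I upward, 0 of 10 possible rises change the grade, and 6 of the 10 meet the protocol's own description of progression.

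Loss of carried-in events from the TEAE count is conditional. It arises if worsening is programmed as a Bayer grade increase or if the carried-in record is only updated. Nor do the documents rank corneal epitheliopathy as the main event of special interest: they name it together with infusion-related reactions, without order.

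The conclusion assumes that some participants enter with, or develop, SPK, and that the compulsory Oxford stage is captured as data. The documents give no frequency of SPK at entry or of progression, so the number of participants affected cannot be estimated.

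**What to change.** Two changes to the SAP:

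1. Add one shift table on the safety set: Oxford stage at rollover baseline by worst on-treatment stage, using the worse eye, with a missing category and the number of participants whose stage rises by two or more. Baseline should be the last examination before the first rollover dose, including a parent-study examination accepted for screening under the Schedule of Activities. This table shows progression however the adverse event is recorded.
2. In SAP 6.3.3, state that worsening of corneal events is not limited to a Bayer grade increase, and that recorded deterioration in Oxford stage counts as worsening, in line with protocol 8.3.1 and 10.3.1. The two-stage rise should be reported in the shift table but not used as a minimum for a TEAE. The sponsor should confirm that the CRF lets a site date such a deterioration in a carried-in event.

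The cost is one table and one sentence, with no new assessment. The corneal TEAE count may rise slightly at Grade 1. No treatment rule changes.

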6.7 Intervention after the End of the Study

There is no planned intervention following the end of the study.

7. Discontinuation of Study Intervention and Participant Discontinuation/Withdrawal

All participants who enter the study should complete all applicable study periods. Participants can be withdrawn from any study period at any time. Withdrawal from the intervention period alone does not constitute withdrawal from the study.

Participants who withdraw from the intervention period for any reason are to be encouraged to remain on the study for follow-up. Participants are expected to participate in follow-up unless they explicitly object. Withdrawal of consent to the intervention period should be documented in the participant's medical record. If the participant does not wish to be followed up further, this additional consent withdrawal for follow-up must also be documented.

7.1 Discontinuation of Study Intervention

It may be necessary for a participant to permanently discontinue study intervention. If study intervention is permanently discontinued, the participant will remain in the study to be evaluated for OS and new anti-cancer treatment. See the SoA for data to be collected at the time of discontinuation of study intervention.

Discontinuation of study intervention for abnormal liver function should be considered by the investigator when a participant meets one of the conditions outlined in Section 6.6 or if the investigator believes that it is in best interest of the participant.

If a clinically significant finding is identified (including, but not limited to changes from baseline in QT interval corrected using Bazett's formula [QTcB] or Fridericia's formula [QTcF]) after enrollment, the investigator or qualified designee will determine if the participant can continue in the study and if any change in participant management is needed. This review of the ECG printed at the time of collection must be documented. Any new clinically relevant finding should be reported as an AE.

See the SoA for data to be collected at the time of intervention discontinuation and follow-up and for any further evaluations that need to be completed.

Study intervention may need to be discontinued for other reasons as specified in the parent study protocols – refer to respective parent study protocol for full set of discontinuation rules.

